7. ADVERSE EVENTS AND TOXICITY MANAGEMENT

7.1. Definitions of Adverse Events, Adverse Reactions, and Serious Adverse Events

7.1.1. Adverse Events

An adverse event (AE) is any untoward medical occurrence in a clinical study subject administered a medicinal product, which does not necessarily have a causal relationship with the treatment. An AE can therefore be any unfavorable and/or unintended sign, symptom, or disease temporally associated with the use of a medicinal product, whether or not considered related to the medicinal product. AEs may also include pre- or post-treatment complications that occur as a result of protocol specified procedures, lack of efficacy, overdose, drug abuse/misuse reports, or occupational exposure. Preexisting events that increase in severity or change in nature during or as a consequence of participation in the clinical study will also be considered AEs.

An AE does not include the following:

- Medical or surgical procedures such as surgery, endoscopy, tooth extraction, and transfusion. The condition that led to the procedure may be an adverse event and must be reported.
- Pre-existing diseases, conditions, or laboratory abnormalities present or detected before the screening visit that do not worsen
- Situations where an untoward medical occurrence has not occurred (e.g., hospitalization for elective surgery, social and/or convenience admissions)
- Overdose without clinical sequelae (see Section 7.7.1)
- Any medical condition or clinically significant laboratory abnormality with an onset date before the consent form is signed and not related to a protocol-associated procedure is not an AE. It is considered to be pre-existing and should be documented on the medical history CRF.

7.1.2. Serious Adverse Events

A serious adverse event (SAE) is defined as an event that, at any dose, results in the following:

- Death
- Life-threatening (Note: The term “life-threatening” in the definition of “serious” refers to an event in which the subject was at risk of death at the time of the event; it does not refer to an event that hypothetically might have caused death if it were more severe.)
- In-patient hospitalization or prolongation of existing hospitalization

- Persistent or significant disability/incapacity
- A congenital anomaly/birth defect
- A medically important event or reaction: such events may not be immediately life-threatening or result in death or hospitalization but may jeopardize the subject or may require intervention to prevent one of the other outcomes constituting SAEs. Medical and scientific judgment must be exercised to determine whether such an event is a reportable under expedited reporting rules. Examples of medically important events include intensive treatment in an emergency room or at home for allergic bronchospasm; blood dyscrasias or convulsions that do not result in hospitalization; and development of drug dependency or drug abuse. For the avoidance of doubt, infections resulting from contaminated medicinal product will be considered a medically important event and subject to expedited reporting requirements.

7.2. Assessment of Adverse Events and Serious Adverse Events

The investigator or qualified subinvestigator is responsible for assessing AEs and SAEs for causality and severity, and for final review and confirmation of accuracy of event information and assessments.

7.2.1. Assessment of Causality for Study Drugs and Procedures

The investigator or qualified subinvestigator is responsible for assessing the relationship to IMP therapy using clinical judgment and the following considerations:

- **No:** Evidence exists that the adverse event has an etiology other than the IMP. For SAEs, an alternative causality must be provided (eg, pre-existing condition, underlying disease, intercurrent illness, or concomitant medication).
- **Yes:** There is reasonable possibility that the event may have been caused by the investigational medicinal product rather than by another etiology.

It should be emphasized that ineffective treatment should not be considered as causally related in the context of adverse event reporting.

The relationship to study procedures (eg, invasive procedures such as venipuncture or biopsy) should be assessed using the following considerations:

- **No:** Evidence exists that the adverse event has an etiology other than the study procedure.
- **Yes:** The adverse event occurred as a result of protocol procedures, (eg., venipuncture)

7.2.2. Assessment of Severity

The severity of AEs will be graded using the modified Common Terminology Criteria for Adverse Events (CTCAE), version 4.03. For each episode, the highest grade attained should be reported.

If a CTCAE criterion does not exist, the investigator should use the grade or adjectives: Grade 1 (mild), Grade 2 (moderate), Grade 3 (severe), Grade 4 (life-threatening) or Grade 5 (fatal) to describe the maximum intensity of the adverse event.

For purposes of consistency with the CTCAE, these intensity grades are defined in [Table 7-1](#) and [Appendix 4](#).

Table 7-1. Grading of Adverse Event Severity

Grade	Adjective	Description
Grade 1	Mild	Asymptomatic or mild symptoms; clinical or diagnostic observations only; intervention not indicated
Grade 2	Moderate	Local or noninvasive intervention indicated; limiting age-appropriate instrumental ADL*
Grade 3	Severe	Severe or medically significant but not immediately life-threatening; hospitalization or prolongation of hospitalization indicated; disabling; limiting self-care ADL**
Grade 4	Life-threatening	Urgent intervention indicated
Grade 5	Death	Death related AE

* Activities of Daily Living (ADL) Instrumental ADL refer to opening preparing meals, shopping for groceries or clothes, using the telephone, managing money, etc.

** Self-care ADL refer to bathing, dressing and undressing, feeding self, using the toilet, taking medications, and not bedridden.

7.3. Investigator Requirements and Instructions for Reporting Adverse Events and Serious Adverse Events to Gilead

Requirements for Collection Prior to Study Drug Initiation:

After informed consent, but prior to initiation of study medication, the following types of events should be reported on the case report form (CRF/eCRF): all SAEs and adverse events related to protocol-mandated procedures.

Adverse Events

Following initiation of study medication, collect all AEs, regardless of cause or relationship, until 30-days after last administration of study IMP must be reported to the CRF/eCRF database as instructed.

All AEs should be followed up until resolution or until the adverse event is stable, if possible. Gilead Sciences may request that certain AEs be followed beyond the protocol defined follow up period.

Serious Adverse Events

All SAEs, regardless of cause or relationship, that occur after the subject first consents to participate in the study (ie, signing the informed consent) and throughout the duration of the study, including the protocol-required post treatment follow-up period, must be reported to the CRF/eCRF database and Gilead PVE as instructed. This also includes any SAEs resulting from protocol-associated procedures performed after informed consent is signed.

Any SAEs and deaths that occur after the post treatment follow-up visit but within 30-days of the last dose of study IMP, regardless of causality, should also be reported.

Investigators are not obligated to actively seek SAEs after the protocol defined follow up period; however, if the investigator learns of any SAEs that occur after study participation has concluded and the event is deemed relevant to the use of IMP, he/she should promptly document and report the event to Gilead PVE.

- All AEs and SAEs will be recorded in the CRF/eCRF database within the timelines outlined in the CRF/eCRF completion guideline.

Electronic Serious Adverse Event (eSAE) Reporting Process

- Site personnel record all SAE data in the eCRF database and from there transmit the SAE information to Gilead PVE within 24 hours of the investigator's knowledge of the event. Detailed instructions can be found in the eCRF completion guidelines.
- If for any reason it is not possible to record the SAE information electronically, ie, the eCRF database is not functioning, record the SAE on the paper serious adverse event reporting form and submit within 24 hours as described above.

Gilead PVE Fax: PPD [REDACTED]
E-mail: PPD [REDACTED]

- As soon as it is possible to do so, any SAE reported via paper must be transcribed into the eCRF Database according to instructions in the eCRF completion guidelines.

- If an SAE has been reported via a paper form because the eCRF database has been locked, no further action is necessary.
- All AEs and SAEs will be recorded in the eCRF database within the timelines outlined in the eCRF completion guideline.
- For fatal or life-threatening events, copies of hospital case reports, autopsy reports, and other documents are also to be submitted by e-mail or fax when requested and applicable. Transmission of such documents should occur without personal subject identification, maintaining the traceability of a document to the subject identifiers.
- Additional information may be requested to ensure the timely completion of accurate safety reports.
- Any medications necessary for treatment of the SAE must be recorded onto the concomitant medication section of the subject's CRF/eCRF and the event description section of the SAE form.

7.4. Gilead Reporting Requirements

Depending on relevant local legislation or regulations, including the applicable US FDA Code of Federal Regulations, the EU Clinical Trials Directive (2001/20/EC) and relevant updates, and other country-specific legislation or regulations, Gilead may be required to expedite to worldwide regulatory agencies reports of SAEs, serious adverse drug reactions (SADRs), or suspected unexpected serious adverse reactions (SUSARs). In accordance with the EU Clinical Trials Directive (2001/20/EC), Gilead or a specified designee will notify worldwide regulatory agencies and the relevant IEC in concerned Member States of applicable SUSARs as outlined in current regulations.

Assessment of expectedness for SAEs will be determined by Gilead using reference safety information specified in the IBs.

All investigators will receive a safety letter notifying them of relevant SUSAR reports associated with any study IMP. The investigator should notify the IRB or IEC of SUSAR reports as soon as is practical, where this is required by local regulatory agencies, and in accordance with the local institutional policy.

7.5. Clinical Laboratory Abnormalities and Other Abnormal Assessments

Laboratory abnormalities are usually not recorded as AEs or SAEs. However, laboratory abnormalities (eg, clinical chemistry, hematology, and urinalysis) independent of the underlying medical condition that require medical or surgical intervention or lead to study drug interruption, modification, or discontinuation must be recorded as an AE, as well as an SAE, if applicable. In addition, laboratory or other abnormal assessments (eg, electrocardiogram, x-rays, vital signs) that are associated with signs and/or symptoms must be recorded as an AE or SAE if they meet the definition of an AE or SAE as described in Sections 7.1.1 and 7.1.2, respectively. If the

laboratory abnormality is part of a syndrome, record the syndrome or diagnosis (i.e., anemia) not the laboratory result (i.e., decreased hemoglobin).

Severity of laboratory abnormality should be recorded and graded according to the modified CTCAE Grading Scale Version 4.03, which can be found in [Appendix 4](#).

For adverse events associated with laboratory abnormalities, the event should be graded on the basis of the clinical severity in the context of the underlying conditions; this may or may not be in agreement with the grading of the laboratory abnormality.

7.6. Toxicity Management

Treatment-emergent toxicities will be noted by the investigator and brought to the attention of the Gilead Sciences Medical Monitor or designee. Whether or not considered treatment -related, all subjects experiencing AEs should be monitored as clinically indicated, until symptoms subside, and until any abnormal laboratory values have resolved or returned to baseline levels or are considered irreversible, or until there is a satisfactory explanation for the changes observed.

All clinical and clinically significant laboratory toxicities will be managed according to uniform guidelines detailed in [Appendix 3](#) and as outlined below.

Grade 3 or 4 clinically significant laboratory abnormalities should be confirmed by repeat testing within 3 calendar days after receipt of the original test results. Grade 3 or 4 clinically significant laboratory abnormalities should be managed as outlined in [Appendix 3](#) and Section 3.4.

Any questions regarding toxicity management should be directed to the Gilead Sciences Medical Monitor or designee.

7.7. Special Situations Reports

7.7.1. Definitions of Special Situations

Special situation reports include all reports of medication error, abuse, misuse, overdose, reports of adverse events associated with product complaints, occupational exposure with an AE, pregnancy reports regardless of an associated AE and AE in an infant following exposure from breastfeeding.

Medication error is any unintentional error in the prescribing, dispensing, or administration of a medicinal product while in the control of the health care provider, subject, or consumer.

Abuse is defined as persistent or sporadic intentional excessive use of a medicinal product by a subject.

Misuse is defined as any intentional and inappropriate use of a medicinal product that is not in accordance with the protocol instructions or the local prescribing information.

An overdose is defined as an accidental or intentional administration of a quantity of a medicinal product given per administration or cumulatively which is above the maximum recommended dose as per protocol or in the product labelling (as it applies to the daily dose of the subject in question). In cases of a discrepancy in drug accountability, overdose will be established only when it is clear that the subject has taken the excess dose(s). Overdose cannot be established when the subject cannot account for the discrepancy except in cases in which the investigator has reason to suspect that the subject has taken the additional dose(s).

Product complaint is defined as complaints arising from potential deviations in the manufacture, packaging, or distribution of the medicinal product.

Occupational exposure is defined as exposure to a medicinal product as a result of one's professional or non-professional occupation.

7.7.2. Instructions for Reporting Special Situations

7.7.2.1. Instructions for Reporting Pregnancies

The investigator should report pregnancies in female study subjects that are identified after initiation of study medication and throughout the study, including the post study drug follow-up period, Gilead PVE using the pregnancy report form within 24 hours of becoming aware of the pregnancy.

Refer to Section 7.3 and the CRF/eCRF completion guidelines for full instructions on the mechanism of pregnancy reporting.

The pregnancy itself is not considered an AE nor is an induced elective abortion to terminate a pregnancy without medical reasons.

Any premature termination of pregnancy (eg, a spontaneous abortion, an induced therapeutic abortion due to complications or other medical reasons) must be reported within 24 hours as an SAE. The underlying medical reason for this procedure should be recorded as the AE term.

A spontaneous abortion is always considered to be an SAE and will be reported as described in Sections 7.1.1 and 7.1.2. Furthermore, any SAE occurring as an adverse pregnancy outcome post study must be reported to Gilead PVE.

The subject should receive appropriate monitoring and care until the conclusion of the pregnancy. The outcome should be reported to Gilead PVE using the pregnancy outcome report form. If the end of the pregnancy occurs after the study has been completed, the outcome should be reported directly to Gilead PVE. Gilead PVE contact information is as follows:

Email: PPD and Fax: PPD

Pregnancies of female partners of male study subjects exposed to Gilead or other study drugs must also be reported and relevant information should be submitted to Gilead PVE using the pregnancy and pregnancy outcome forms within 24 hours. If the end of the pregnancy occurs after the study has been completed, the outcome should be reported directly to Gilead PVE, fax number PPD or email PPD

Refer to [Appendix 5](#) for Pregnancy Precautions, Definition for Female of Childbearing Potential, and Contraceptive Requirements.

7.7.2.2. Reporting Other Special Situations

All other special situation reports must be reported on the special situations report form and forwarded to Gilead PVE within 24 hours of the investigator becoming aware of the situation. These reports must consist of situations that involve study IMP and/or Gilead concomitant medications, but do not apply to non-Gilead concomitant medications.

Special situations involving non-Gilead concomitant medications does not need to be reported on the special situations report form; however, for special situations that result in AEs due to a non-Gilead concomitant medication, the AE should be reported on the AE form.

Any inappropriate use of concomitant medications prohibited by this protocol should not be reported as “misuse,” but may be more appropriately documented as a protocol deviation.

Refer to Section [7.3](#) and the CRF/eCRF completion guidelines for full instructions on the mechanism of special situations reporting.

All clinical sequelae in relation to these special situation reports will be reported as AEs or SAEs at the same time using the AE CRF/eCRF and/or the SAE report form. Details of the symptoms and signs, clinical management, and outcome will be reported, when available.

8. STATISTICAL CONSIDERATIONS

8.1. Analysis Objectives and Endpoints

8.1.1. Analysis Objectives

[figure not shown]
The primary objective of this study is:

- To assess the efficacy of filgotinib, GS-9876 and GS-4059 in adult subjects with active SjS.

The secondary objectives of this study are:

- To assess the safety and tolerability of filgotinib, GS-9876 and GS-4059 in adult subjects with active SjS
- To assess the effect of filgotinib, GS-9876 and GS-4059 on patient reported outcomes in active SjS, including fatigue, disability and quality of life

The exploratory objectives of this study are:

8.1.2. Primary Endpoint

The primary endpoint is the proportion of subjects at who fulfill response criteria as outlined in Section 2.

[figure not shown]
8.1.3. Secondary Endpoint

Secondary endpoints are:

- Change from baseline in ESSDAI at Week 12
- Change from baseline in ESSPRI at Week 12
- Change from baseline in ESSDAI at Week 24
- Change from baseline in ESSPRI at Week 24

8.1.4. Exploratory Endpoints

8.2. Analysis Conventions

8.2.1. Analysis Sets

8.2.1.1. All Randomized

The All Randomized Analysis Set includes all subjects who are randomized in the study. This is the primary analysis set for by-subject listings.

8.2.1.2. Efficacy

The primary analysis set for efficacy analyses will be the Full Analysis Set, which includes all randomized subjects who received at least one dose of study drug.

8.2.1.3. Safety

The primary analysis set for safety analyses will be the Safety Analysis Set, which includes all subjects who received at least one dose of study drug.

8.2.1.4. Pharmacokinetics

8.2.1.4.1. PK Substudy Analysis Set

8.2.1.4.2. PK Analysis Set

The primary analysis set for PK analyses will be the PK Analysis Set, which includes all subjects in the Safety Analysis Set who have at least 1 non-missing PK concentration data for GS-9876, filgotinib, GS-4059, and/or their metabolite(s).

8.2.1.5. Biomarker

The primary analysis set for biomarker analyses will be the Biomarker Analysis Set, which includes all subjects in the Safety Analysis Set who have at least one evaluable measurement available at any time point for a given biomarker of interest.

8.3. Data Handling Conventions

Pharmacokinetic concentration values and PK parameter values below the limit of quantitation (BLQ) will be presented as “BLQ” in the data listings. BLQ values that occur prior to the first dose will be treated as 0, BLQ values at all other time points will be treated as 1/2 of the lower limit of quantitation (LLOQ).

Laboratory data that are continuous in nature but are less than the lower limit of quantitation or above the upper limit of quantitation will be imputed to the value of the lower or upper limit minus or plus one significant digit, respectively (eg, if the result of a continuous laboratory test is < 20, a value of 19 will be assigned; if the result of a continuous laboratory test is < 20.0, a value of 19.9 will be assigned).

8.4. Demographic Data and Baseline Characteristics

Demographic and baseline measurements will be summarized using standard descriptive statistics including sample size, mean, SD, median, Q1, Q3, minimum, and maximum for continuous variables and number and percentages of subjects for categorical variables.

Demographic summaries will include sex, race/ethnicity, and age.

Baseline characteristics will include a summary of at least PROs, ESSDAI, disease duration (time from diagnosis), CCI, 28-joint count, current or prior use of DMARD(s), and oral corticosteroids.

8.5. Efficacy Analysis

8.5.1. Primary Analysis

The primary endpoint is the proportion of subjects fulfilling response criteria (as outlined in Section 2). The primary analysis will consist of a superiority test of each of filgotinib, GS-9876 or GS-4059 compared to placebo, respectively. CMH approach adjusting for the randomization stratification factors will be used for the hypothesis testing at the 2-sided 0.05-level.

8.5.2. Secondary and Exploratory Analyses

CCI
[REDACTED]

8.6. Safety Analysis

All safety analyses will be performed using the Safety Analysis Set.

Safety will be evaluated by assessment of clinical laboratory tests, physical examinations, vital signs measurements at various time points during the study, and by the documentation of AEs.

All safety data collected on or after the date that study drug was first dispensed up to the date of last dose of study drug + 30 days will be summarized by treatment group (according to the IMP study drug received).

8.6.1. Extent of Exposure

A subject's extent of exposure to study drug will be generated from the study drug administration page of the eCRF. Exposure data will be summarized by treatment group.

Duration of exposure to study drug will be expressed as the number of weeks between the first and last dose of the study drug, inclusive, regardless of temporary interruptions in study drug administration and summarized by treatment group.

8.6.2. Adverse Events

Clinical and laboratory adverse events will be coded using the Medical Dictionary for Regulatory Activities (MedDRA). System Organ Class (SOC), High-Level Group Term (HLGT), High-Level Term (HLT), Preferred Term (PT), and Lower-Level Term (LLT) will be attached to the clinical database.

Treatment-emergent adverse events (TEAEs) are defined as one or both of the following:

- Any AEs with an onset date on or after the study drug start date and no later than 30 days after permanent discontinuation of study drug.
- Any AEs leading to premature discontinuation of study drug.

Summaries (number and percentage of subjects) of treatment-emergent adverse events (by SOC, and PT) will be provided by treatment group.

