3.4.2. Study Drug Discontinuation Considerations

The Medical Monitor should be consulted prior to study drug discontinuation whenever feasible.

Study medication should be permanently discontinued in the following instances:

- Any opportunistic infection
- Any serious infection that requires antimicrobial therapy or hospitalization, or any infection that meets SAE reporting criteria.
- Complicated herpes zoster infection (with multi-dermatomal, disseminated, ophthalmic, or CNS involvement)
- Unacceptable toxicity, or toxicity that, in the judgment of the investigator, compromises the subject's ability to continue study-specific procedures or is not considered to be in the subject's best interest
- Need for prohibited concomitant medication (see Section 5.8)

- Subject request to discontinue for any reason
 - Subject noncompliance, as per judgment of investigator
 - Request from Gilead, a regulatory agency or an IRB or IEC
 - Female subject becomes pregnant during the study; refer to Section 7.7.2.1
 - Positive HCV VL
 - Investigator discretion
 - Laboratory criteria:
After becoming aware of any of the below described abnormal laboratory values at any time, an unscheduled visit should occur within 3 to 7 days, with the exception of creatinine clearance which should be retested within 7 to 14 days. Retest may be obtained sooner if medically indicated per investigator judgment. If the laboratory abnormality is confirmed by the retest, then study medication should be discontinued and further care of the subject should be directed per the investigator.
 - total white blood cell (WBC) count < 2000 cells/mm³ (SI: < 2.0x10⁹ cells/L)
 - neutrophil count < 1000 neutrophils/mm³ (SI: < 1.0x10⁹ cells/L)
 - hemoglobin < 8.0 g/dL (SI: < 80 g/L)
 - platelet count < 75,000 platelets/mm³ (SI: < 75.0x10⁹ cells/L)
 - AST or ALT elevation:
 - > 3xULN with at least 1 total bilirubin value >2xULN
 - > 3xULN with elevated international normalized ratio (INR)
 - > 5xULN, regardless of total bilirubin or accompanying symptoms
- Note:** For the above described AST or ALT elevations, additional investigations (such as: review of ethanol, recreational drug use, dietary supplement consumption; testing for acute hepatitis A, B or C infection and biliary tract imaging) should be promptly considered by the investigator; these subjects should be discussed with the study Medical Monitor.
- estimated creatinine clearance < 40 mL/min based on the Cockcroft-Gault formula

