7. SAFETY ANALYSES

The safety analyses will be performed for the placebo-controlled treatment period up to Week 24, and for the entire study duration. Analyses for these periods will be presented by the treatment groups specified in Section 3.

For the analyses of adverse events (AEs) that include data after Week 24 the exposure-adjusted analyses will be presented.

For the AEs, laboratory results and concomitant medication data, the collection/start date will be used to determine which reporting period the record belongs to. For other parameters collected on CRFs, the nominal visits will be used.

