7.1.5. Treatment-Emergent Adverse Events

7.1.5.1. Definition of Treatment-Emergent Adverse Events

Treatment-emergent adverse events (TEAEs) of the entire study duration are defined as 1 or both of the following:

- Any AEs with an onset date on or after any study drug start date and no later than 30 days after permanent discontinuation of any study drug
- Any AEs leading to premature discontinuation of study drug.

TEAEs up to Week 24 are defined as 1 or both of the following:

- Any AEs with an onset date on or after Day 1 and no later than the day before the Week 24 treatment start date.
- For subjects who discontinued treatment prior to Week 24 visit, any AEs with an onset date no later than 30 days after permanent discontinuation of study drug

TEAEs of active treatment are defined similarly as the definition of the entire study duration, except that active study drug instead of any study drug will be used:

- Any AEs with an onset date on or after the first dose of active study drug and no later than 30 days after permanent discontinuation of active study drug.

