7.1.6. Summaries of Adverse Events and Deaths

TEAEs will be summarized based on the Safety Analysis Set.

The tables will be presented by treatment period: placebo-controlled period (up to Week 24) and active treatment period. The overall summary of TEAEs will also be provided for the entire study duration.

The number and percentage of subjects who experienced at least 1 TEAE will be provided and summarized by SOC, HLT, PT, and treatment group. For other AEs described below, summaries will be provided by SOC, PT, and treatment group:

- All TEAEs
- TEAEs of Grade 3 or higher (by maximum severity)
- All TE treatment-related AEs
- TE treatment-related AEs of Grade 3 or higher (by maximum severity)
- All TE SAEs
- All TE treatment-related SAEs
- All TEAEs leading to premature discontinuation of study drug
- All TEAEs leading to premature discontinuation of study
- All TEAEs leading to death (i.e. outcome of death)

A brief, high-level summary of AEs described above will be provided by treatment group and by the number and percentage of subjects who experienced the above AEs. All deaths observed in the study will also be included in this summary.

Multiple events will be counted only once per subject in each summary. Adverse events will be summarized and listed first in alphabetic order of SOC and HLT within each SOC (if applicable), and then by PT in descending order of total frequency within each SOC. For summaries by severity grade, the most severe grade will be used for those AEs that occurred more than once in an individual subject during the study.

In addition to the above summary tables, all TEAEs and TE treatment-related AEs will be summarized by PT only, in descending order of total frequency.

The data listings will be provided for the following:

- All AEs, indicating whether the event is treatment emergent

- All AEs of Grade 3 or higher
- SAEs
- Deaths
- AEs leading to premature discontinuation of study drug
- AEs leading to premature discontinuation of study

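### Week 0–24 adverse events are summarised only as crude percentages, although early stoppers are counted for a shorter time; exposure-adjusted results should be added for this period too

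*Protocol*

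**What the plan says.** **Summary measure.** Protocol 8.6.2: "Summaries (number and percentage of subjects) of treatment-emergent adverse events (by SOC, and PT) will be provided by treatment group". SAP 7.1.6 agrees ("The number and percentage of subjects who experienced at least 1 TEAE will be provided"), bases the tables on the Safety Analysis Set (all dosed subjects), and tabulates the controlled period separately: "The tables will be presented by treatment period: placebo-controlled period (up to Week 24) and active treatment period". SAP 7.1.7 also uses number and percentage for events of special interest.

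**Counting window.** SAP 7.1.5.1 defines events up to Week 24 in two parts. The first is "Any AEs with an onset date on or after Day 1 and no later than the day before the Week 24 treatment start date". The second, which covers those stopping treatment before the Week 24 visit, counts "any AEs with an onset date no later than 30 days after permanent discontinuation of study drug". Protocol 8.6 cuts summarised safety data at the same point. Protocol 7.3 requires sites to "collect all AEs, regardless of cause or relationship, until 30-days after last administration of study IMP"; SAEs are collected for longer.

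**Exposure adjustment.** SAP 7: "For the analyses of adverse events (AEs) that include data after Week 24 the exposure-adjusted analyses will be presented". Protocol 6.3 and SAP 1.2 move placebo subjects to active drug at Week 24.

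**Stopping.** Protocol 3.4.2 opens its list with "Study medication should be permanently discontinued in the following instances". The list covers infections, toxicity and confirmed laboratory abnormalities, but also subject request, noncompliance and sponsor request.

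**The concern.** Safety is a secondary objective, and Weeks 0–24 are the only period with a concurrent placebo group. A crude percentage compares arms fairly only if subjects are observed for similar lengths of time. Here a subject who stops at Week 4 is counted for about 8 weeks and a subject who continues for 24, yet both weigh the same in the denominator. If one arm has more early stopping, its percentages for many event types can be lower with no difference in risk.

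The SAP plans an adjustment for unequal exposure but applies it only where data after Week 24 enter, and so not to the table that has a control. The Week 24 unblinded safety results go to a sponsor team (SAP 2.3), so these tables will be read comparatively even though no test is planned.

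**Working it through.** The plan gives no figure to reproduce, and the documents give no discontinuation or event rates. The rates below are therefore assumptions.

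**Inputs from the documents:** 24-week window for subjects who continue; stop time plus 30 days for those who stop (SAP 7.1.5.1); about 35 subjects per arm (Protocol 8.9).

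**Inputs assumed:** the same constant event hazard λ in both arms, 0.25, 0.5, 1 or 2 per patient-year; all stoppers stop at Week 4, 8 or 12, independently of the event studied; stopping of 20% vs 5%, 30% vs 10%, or 40% vs 10%.

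**Formulas** (52.18 weeks per year)
- Probability of a counted event in a window of w weeks: P(w) = 1 − exp(−λw/52.18)
- Expected crude proportion with a fraction d stopping at week s: (1 − d)·P(24) + d·P(s + 30/7)

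**Worked example** (λ = 1, stop at Week 4, 30% vs 10%)
- Continuer: P(24) = 1 − exp(−0.460) = 36.9%
- Stopper: window 4 + 4.29 = 8.29 weeks; P = 1 − exp(−0.159) = 14.7%
- 30% stopping: 0.70 × 36.87 + 0.30 × 14.68 = 30.2%
- 10% stopping: 0.90 × 36.87 + 0.10 × 14.68 = 34.6%
- Gap: 4.4 percentage points, or 35 × 0.044 ≈ 1.6 subjects, at identical risk. Mean windows are 19.3 and 22.4 weeks.
- Standard error of a difference between two such percentages at 35 per arm: √(0.302 × 0.698/35 + 0.346 × 0.654/35) ≈ 11 points

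**Whole grid (36 combinations)**

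| Hazard per patient-year | Gap, subjects of 35 |
|---|---|
| 0.25 | 0.2–0.7 |
| 0.5 | 0.3–1.4 |
| 1 | 0.5–2.3 |
| 2 | 0.7–3.5 |

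The relative shortfall runs from 3.5% to 20.6%. The arm with more stopping is lower in every cell. With equal stopping at equal times there is no gap.

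**When the stop is caused by an adverse event.** That event starts before the stop, so it is inside the window and is counted. In the worked example, if every stop is caused by an event, the percentage with any event is 0.30 + 0.70 × 0.369 = 55.8% against 0.10 + 0.90 × 0.369 = 43.2%. The arm with more stopping now shows more. The shortfall is confined to other or later events: a subject stopped for a cytopenia stays in the infection and bleeding denominators with at most 30 more days of counting.

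**Does a first-event rate repair it?** Under a constant hazard it does: expected first events divided by patient-years at risk equals λ in both arms whatever the stopping. Under a front-loaded hazard it does not. Take 2.6 per year for 4 weeks and 0.3 afterwards, the same in both arms, with stopping at Week 4 of 30% vs 10%:
- Rates: 0.2490/0.2971 = 83.8 against 0.2628/0.3431 = 76.6 per 100 patient-years
- Crude percentages: 24.9% against 26.3%

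Here the rate puts the arm with more stopping higher, while the crude percentages differ by only 1.4 points.

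**The case against.** The best defence is that crude percentages to a fixed Week 24 horizon are not an error in a small proof-of-concept study. The plan also shows unequal follow-up openly. SAP 4.2.1 gives the percentage exposed through successive weeks by arm, and SAP 4.1 gives completion of study drug to Weeks 12 and 24 with reasons. SAP 7.1.6 tabulates events leading to discontinuation, puts all deaths in the high-level summary whenever they occur, and lists every event. The gaps above are small against a standard error of about 11 points, and no test of adverse events is planned. Exposure adjustment after Week 24 has its own reason: switched placebo subjects and those on active drug from Day 1 differ in duration by design.

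Most of this stands, and it limits the weight of the point. It does not remove it: the exposure and disposition tables let a reader see an imbalance but do not say what it does to incidence.

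From the toxicity criteria in Protocol 3.4.2, a reader might infer that the more toxic arm will necessarily show lower percentages. The documents do not support that. The event that triggers a stop is counted, any-event percentages can rise as shown, and the same list includes reasons unrelated to toxicity.

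**Conclusion.** The point holds in conditional form. For Weeks 0–24 the plan offers only crude percentages over windows that shorten when a subject stops early. If stopping differs between arms, the arm with more early stopping is expected to show a lower percentage, at the same risk, for events other than the one that caused the stop.

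The size is modest: about 0.2–3.5 subjects of 35 on the assumed grid, and under one subject at 0.25 events per patient-year, the setting closest to rare events of special interest. The largest figure needs 40% stopping, all at Week 4, with 2 events per patient-year.

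A reader might go further and call the planned summary biased in favour of the active drugs. The documents do not show that: they give no stopping rates, and without unequal stopping the distortion between arms is absent. This is a cheap improvement to a descriptive analysis, not a flaw that invalidates the safety tables.

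**What to change.** Extend the exposure-adjustment sentence in SAP 7 to the placebo-controlled period, at least for all treatment-emergent events, SAEs, infections and the other events of special interest. For each arm, report subjects with a first event per patient-year at risk, with a 95% CI, beside the crude number and percentage. Time at risk runs from first dose to the first event or the end of that subject's Week 24 counting window. State that window end explicitly for subjects with no Week 24 treatment start, because the first part of the SAP 7.1.5.1 definition gives them none and only the second part does.

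Add a note that these rates assume a roughly constant hazard and must be read with the crude percentages, since events clustered early can push them the other way. Alternatively, or in addition, give a time-to-first-event (cumulative incidence) estimate at Week 24, censored at the end of the counting window. That needs no constant hazard, but it still assumes that stopping is unrelated to the later risk of the event.

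The cost is a few extra tables from dates already collected, using a type of analysis the SAP already plans. There are no new data and no change in conduct. Intervals will be wide at about 35 subjects per arm.
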